	 To examine the association between peak brain tissue PO2 during hyperbaric treatment and favorable outcome at 6-months (measured by the GOS-E).
	6. Determine the most effective hyperbaric oxygen therapy paradigm using an alternative scoring of the GOS-E (approximately continuous severity adjusted scoring of the GOS-E).
a se incl are nor	individuals, aged 16 to 65, presenting to a collaborating institution with evere TBI defined as a GCS score 3 to 8 are potential candidates for lusion. Subjects with a GCS score of 7 or 8 with a Marshall CT score = 1 e excluded. Subjects with a GCS score of 3 AND bilateral mid-position, nreactive pupils are excluded because of their grim prognosis and the t that it is doubtful any treatment could have a neuroprotective effect.
Phase: II	
Intervention: six (NE The Abs day	ere are eight treatment arms. Participants will be randomized to one of hyperbaric oxygen (HBO) treatment groups, one normobaric hyperoxia BH) treatment group, or one control (no hyperoxia treatment) group. e six hyperbaric oxygen treatment groups are: 1.5 Atmospheres solute (ATA) for 60 minutes twice a day; 2.0 ATA for 60 minutes twice a y; 2.5 ATA for 60 minute twice a day; 1.5 ATA for 60 minutes followed by H for 3 hours twice a day; 2.0 ATA for 60 minutes with NBH for 3 hours

	twice a day; 2.5 ATA for 60 minutes with NBH for 3 hours twice a day, and NBH for 4.5 hours twice a day.
Study Duration:	Anticipated 60 months
Participant Duration:	6 months

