OB.	JECTIVES	ENDPOINTS	JUSTIFICATION FOR ENDPOINTS					
Prir	mary							
effe par pro	definitively determine the most ective hyperbaric oxygen therapy radigm and to predict the obability that this treatment will ult in a successful Phase III trial.	Proportion of subjects with favorable outcome at 6-months (Severity adjusted GOS-E)	GOS-E is the most frequently used functional outcome measure for TBI studies.					
Sec	condary							
1.	Determine the effect of HBO treatment on the duration of ICP elevation.	The level and duration of intracranial hypertension (ICP>22 mmHg) will be measured.	Intracranial hypertension is the leading cause of death and deterioration in the first week following TBI (Jull, 2000).					
2.	Determine the effect of HBO treatment on therapeutic intensity level (TIL) scores for controlling intracranial pressure (ICP).	Therapeutic intensity level (TIL) scores. This documents the level of therapies used to control ICP and will be tracked daily during the treatment period.	TIL scores will quantify the intensity of treatment required to control ICP between treatment groups.					
3.	Determine the effect of HBO treatment on brain tissue partial pressure of oxygen (PO2)monitoring.	The level and duration of brain tissue hypoxia (brain tissue PO2 <20 mmHg).	Brain tissue PO2 levels <20mmHg correlate with poor outcome in severe TBI (VanDen Brink, 2000).					
4.	Compare the type and incidence of SAEs between hyperoxia treatment arms and control.	SAEs include: Pneumothorax secondary to HBO, pulmonary dysfunction defined as PaO2/FiO2 (PF) ratio<200, pneumonia, and seizures during HBO.	Special scrutiny is required for complications related to hyperoxia treatment.					

5.	Estimate the effect of peak brain tissue PO2 during hyperbaric oxygen treatment on GOS-E at 6-months.	Dichotomized GOS-E.	Level of O2 achieved in the brain during HBO treatment may correlate with outcome.

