6.	Determine the most effective hyperbaric oxygen therapy paradigm using an alternative scoring of the GOS-E.	A sliding approximately continuous severity adjusted scoring of the GOS-E that measures the distance from favorable outcome cut point. See statistical analysis plan (SAP) for specific scoring algorithm and analytic plan.	Scoring the severity adjusted GOS-E as a dichotomy does not account for better recovery (e.g. upper and lower good recovery are scored the same). Further, simulations indicate that using the approximately continuous severity adjusted scoring of the GOS-E provides better probability of selecting the optimal therapy.

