The subjects are connected to the hyperbaric ventilator at least 15 minutes prior to being pressurized in the HBO chamber. Ventilatory parameters are set and stabilized, and arterial blood gases are checked to verify that the ventilator parameters are appropriate. If secretions are present, the subject is suctioned thoroughly prior to the HBO treatment. Bilateral myringotomy is performed prior to the first HBO treatment. The myringotomy can be accomplished with an 18-gauge spinal needle in the anterior inferior quadrant of the tympanic membrane. The tympanic membrane should be checked each day to assure patency of the myringotomies. This procedure reduces middle ear barotrauma and thus avoids the painful stimulation which raises ICP (Rockswold 1992). A myringotomy will not be performed if there is blood in the external canal or otorrhea present. A hyperbaric pre-treatment checklist is maintained and all items performed and checked off prior to the subject entering the HBO chamber.

Monitoring of the Severe TBI Subject During HBO Treatment.

Subject monitoring and safety within the HBO chamber is of the utmost importance (Gossett 2010, Rockswold 1985, Weaver 1988, Weaver 1999, Weaver 1999). The hyperbaric chamber becomes an extension of the critical care environment. Routine monitoring of the subject includes continuous heart rate, blood pressure, electrocardiogram, and central venous pressures as needed. Intracranial monitoring, including ICP will continue throughout the HBO treatment. Brain tissue PO2 and brain temperature monitoring will be optional. ICP will be monitored using an intraventricular catheter or parenchymal monitor . If the subject has an intraventricular catheter and in a monoplace chamber, a pressure transducer is connected to the ventriculostomy line inside the HBO chamber. CSF is allowed to flow from the ventriculostomy to the transducer which converts the fluid pressure to a digital signal. This signal is transmitted through the chamber door to the outside monitors via electrical penetrations. A system will allow the attendant on the outside of the monoplace chamber to turn the ventriculostomy stopcock valve either open for draining (if ICP is elevated) or closed for intermittent ICP monitoring.

Management of the Severe TBI Subject in the HBO Chamber Monoplace Chamber

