10.2 ABBREVIATIONS

10.3 PROTOCOL AMENDMENT HISTORY

Section of Change	Version 5	Version 6	Rationale
Title Page	Version Number: 5 – April 5th 2019	Version Number: 6 - November 8th 2019	
Header	HOBIT Protocol Version 5	HOBIT Protocol Version 6	
Table of Contents			
Signatur e Page	5, date April 5th, 2019	6, dated November 8th, 2019	
1.1		6. Determine the most effective hyperbaric oxygen therapy paradigm using an alternative scoring of the GOS-E (approximately continuous severity adjusted scoring of the GOS-E).	Better power and sample size properties for continuou s measure compared to dichotomy . This will provide additional informatio n for learning the relative efficacy of

			novel therapy relative to control
3		 6. Determine the most effective hyperbaric oxygen therapy paradigm using an alternative scoring of the GOS- E. A sliding approximately continuous severity adjusted scoring of the GOS-E that measures the distance from favorable outcome cut point. See statistical analysis plan (SAP) for specific scoring algorithm and analytic plan. Scoring the severity adjusted GOS- E as a dichotomy does not account for better recovery (e.g. upper and lower good recovery are scored the same). Further, simulations indicate that using the approximately continuous severity adjusted scoring of the GOS-E provides better probability of selecting the optimal therapy. 	Better power and sample size properties for continuous measure compared to dichotomy. This will provide additional informatio n for learning the relative efficacy of novel therapy relative to control
5.1	Written, informed consent from LAR	Written, informed consent from LAR or eligible for exception from informed consent	Clarificatio n to include EFIC procedures
5.4	How potential participants will be identified and approached: Trained	How potential participants will be identified and approached: Trained research coordinators will monitor all trauma presentations	Clarificatio n to include EFIC procedures

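### Secondary objective 5 ties peak brain tissue PO2 to a dichotomized GOS-E only, although the protocol already derives a more informative severity-adjusted score for objective 6

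*Protocol*

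**What the plan says.** In the objectives table of protocol section 3, secondary objective 5 reads "Estimate the effect of peak brain tissue PO2 during hyperbaric oxygen treatment on GOS-E at 6-months". The endpoint column beside it contains only "Dichotomized GOS-E". Synopsis endpoint 5 (section 1.1) agrees that the outcome is binary: "To examine the association between peak brain tissue PO2 during hyperbaric treatment and favorable outcome at 6-months".

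Row 6 of the same table takes another view of the scale. It says "Scoring the severity adjusted GOS-E as a dichotomy does not account for better recovery", and it sets as endpoint "A sliding approximately continuous severity adjusted scoring of the GOS-E that measures the distance from favorable outcome cut point". The scoring algorithm is left to the SAP. The rationale in section 10.3 for adding this objective is that the continuous measure has more power and a more favorable sample size than the dichotomy. The protocol uses the score only to choose the treatment paradigm.

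On the exposure, section 6.2.1 says "Brain tissue PO2 and brain temperature monitoring will be optional", and section 8.1 confines recording to sites that use such monitoring. A peak during hyperbaric treatment exists only for subjects treated in a chamber.

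**The concern.** The protocol gives its own reason for preferring the finer score, yet does not carry it over to objective 5, where subjects are scarcest. Control and NBH-only subjects have no hyperbaric peak, and HBO subjects without a brain tissue probe drop out as well. Collapsing the outcome to two values discards information that the trial will already hold for objective 6.

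At stake is precision. The estimated relation between tissue oxygen and outcome will be less certain than the data allow, and a real relation is somewhat more likely to be missed. The primary analysis, arm selection and stopping rules are not affected.

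**Working it through.** **Stated figure.** There is none to reproduce. The protocol gives no sample size, power, test or significance level for objective 5. The table of operating characteristics in section 9.2 concerns the primary endpoint.

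**Inputs from the protocol**
- Maximum 200 randomized (section 4.1).
- Burn-in of 56 (section 6.3): 11 control, 9 in the 2.5 ATA+NBH arm and 6 in each of the other six active arms, so 11 + 6×6 + 9 = 56. The six HBO arms hold 5×6 + 9 = 39. Later numbers depend on the adaptive allocation.
- Favorable rate: 0.40 for control and up to 0.55 in the small-effect scenario (section 9.2). On a sliding dichotomy of the GOS in the earlier HBO trial it was 45.6% and 58.3% (section 2.1).
- Mortality of 40% (section 8.4.2), used as the share in the combined vegetative-or-death category.
- Sliding cut points of 7, 6, 5 and 4 by prognostic band (section 9.1).

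**Assumptions.** 40 to 80 monitored HBO subjects; a shift across the whole scale; the other six GOS-E categories equally frequent at 10% each.

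**Step 1: efficiency.** Under proportional odds with a modest effect, a binary endpoint with favorable rate p has efficiency 3p(1−p) / (1 − Σpᵢ³) relative to the full ordinal scale.
- Denominator: 1 − (0.4³ + 6×0.1³) = 1 − 0.070 = 0.930.
- p = 0.40: 0.720/0.930 = 0.774.
- p = 0.45 or 0.55: 0.7425/0.930 = 0.798.
- p = 0.50: 0.750/0.930 = 0.806.

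The dichotomy therefore keeps about 77% to 81% of the information. Equal information would take 1/0.806 = 1.24 to 1/0.774 = 1.29 times as many subjects. On a common scale, standard errors are √1.24 = 1.11 to √1.29 = 1.14 times as large, which matters for an objective worded as estimation. With a 30% floor or seven equal categories, efficiency is 0.735 to 0.778.

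**Step 2: power.** Simulation with 4,000 runs per cell and a two-sided 0.05 correlation test. A normal latent outcome has correlation r with standardized peak PO2 and 0.5 with prognosis. It is cut into the seven categories above, with four equal prognostic bands and cut points 4 to 7. The score is GOS-E minus the band's cut point. Entries are percent power, dichotomy v score, with the gain in brackets.

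| Monitored HBO subjects | r = 0.2 | r = 0.3 | r = 0.4 |
|---|---|---|---|
| 40 | 19.1 v 24.1 (5.0) | 36.8 v 47.7 (10.9) | 59.8 v 75.8 (16.0) |
| 60 | 25.8 v 33.0 (7.2) | 51.9 v 66.0 (14.1) | 78.7 v 90.6 (11.9) |
| 80 | 32.9 v 43.0 (10.1) | 65.0 v 79.5 (14.5) | 89.7 v 97.0 (7.3) |

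The gain is roughly 5 to 16 points.

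**Step 3: sensitivity.** The setup of step 2 gives a favorable rate of about 33%, below the 0.40 to 0.55 of step 1. At p = 0.33 the efficiency is 3×0.33×0.67/0.930 = 0.71, so those cells somewhat favor the score. Keeping the 40% floor but giving the six upper categories 4%, 4%, 6%, 8%, 16% and 22% raises the favorable rate to about 48%. Over the same nine cells (6,000 runs each) the gain is then about 4 to 13 points. The direction and order of size hold.

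**The case against.** The strongest reply is that nothing here is wrong. Row 5 and synopsis endpoint 5 agree with each other. A dichotomized outcome also matches the primary endpoint, the success rules in section 9.1 and the phase III target of a rate of good neurological outcome. Asking whether tissue oxygen tracks the outcome on which the trial is judged is coherent. This stands.

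Section 9.3 says the secondary models, including the one for peak PO2, are in the SAP, which may already hold a supportive analysis. That is possible, but the protocol names the endpoint itself, and it names only the dichotomy.

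The row 6 rationale concerns selecting a therapy, not an exposure association among HBO subjects, and the simulated score is a guess at an algorithm held in the SAP. Both points stand. They limit how firmly the loss can be sized, though the efficiency argument does not depend on arm selection. The score also has costs: it treats GOS-E steps as equal, has a heavy floor, and its range differs by prognostic band.

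Three stronger readings are tempting, and the protocol does not support them.
- **That the weakness feeds the go/no-go decision.** The sentences on that decision in sections 4.2 and 9.3 concern treatment effects on ICP, TIL and brain tissue PO2. The link between peak PO2 and outcome is in a separate paragraph that makes no such claim.
- **That a null result would be due to the outcome coding.** With 40 subjects and r = 0.3 the score itself has only about 48% power. Small numbers from optional monitoring limit the analysis under either coding.
- **That the dichotomy should be replaced.** Enrollment had begun (section 10.1.1.4), and demoting a prespecified outcome that matches the primary endpoint during the trial is debatable.

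**Conclusion.** The point holds as a low-severity efficiency weakness, not as an error or a contradiction. Objective 5 fixes a binary outcome, while the protocol derives a finer score and credits it with better power.

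The loss is about 19% to 23% of the information under the assumptions of step 1, or roughly 5 to 16 points of power with 40 to 80 monitored HBO subjects. The number monitored, the strength of the relation, the GOS-E distribution and the form of the score are all assumed. If peak PO2 acts only at the cut point, the loss is smaller or absent. It also shrinks where power is already near its floor or ceiling.

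**What to change.** In row 5 of section 3 and in synopsis endpoint 5, keep the dichotomized GOS-E for consistency with the primary endpoint. Add the approximately continuous severity-adjusted score of objective 6 as a second prespecified outcome for the peak PO2 association. A proportional-odds model on the GOS-E with the IMPACT probability as covariate would serve equally well. Report both with interval estimates. The same edit should say whether the dichotomy in row 5 is the sliding one of section 9.1, since that row does not.

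The cost is a line in each place, a matching model in the SAP, and one more secondary analysis. No new data are needed. The slope on the added score is less directly interpretable than an odds of favorable outcome, which is a further reason to keep the dichotomized result beside it.

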4 STUDY DESIGN

4.1 OVERALL DESIGN

This trial is designed as multicenter, prospective, randomized, adaptive phase II clinical trial. All individuals presenting at an enrolling site with a severe TBI defined as a GCS score of 3-8 (age 16 to 65 years) are initially eligible for inclusion. Subjects with a GCS score of 7 or 8 and a Marshall CT score of 1, as well as subjects with a GCS score of 3 and bilaterally mid position, non-reactive pupils will be excluded. No exclusion criteria will be based on race, ethnicity, or gender. The trial design is adaptive. The primary outcome is a sliding dichotomized adjusted GOS-E at 6 months. However, clinical data from *Baseline*, Day 30, and Day 90 will be used to predict 6-month data. The trial will explore *seven* different active treatment arms for relative efficacy in comparison to the control arm. *Four* pressures (*1.0*, 1.5, 2.0 and 2.5 ATA) and HBO with or without NBH will be studied. *NBH will also be evaluated without HBO, serving both as a treatment arm and a control for the effect of pressure.* Utilizing *the most promising* treatment arm demonstrating improvement in outcome in a subsequent phase III trial will be calculated. *If the probability is > 50%, this treatment arm will be compared for superiority to the control in a future phase III trial.* The maximum number of subjects to be randomized is 200.

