1.1 SYNOPSIS

Title:	Hyperbaric Oxygen Brain Injury Treatment (HOBIT) Trial: A Multicenter, Randomized, Prospective Phase II Adaptive Clinical Trial Evaluating the Most Effective Hyperbaric Oxygen Treatment Paradigm for Severe Traumatic Brain Injury				
Study Description:	There continues to be an overarching problem of high mortality and poor outcome for victims of severe traumatic brain injury (TBI). Preclinical and clinical investigations indicate that hyperbaric oxygen (HBO) has a positive impact on reducing brain injury and improving outcomes in severe TBI. By markedly increasing oxygen (O2) delivery to the traumatized brain, HBO can reverse the lack of O2 that precipitates cellular energy failure and subsequent brain cell death. However, prior to a formal phase III definitive efficacy study, important information is required regarding optimizing the HBO treatment schedule to be instituted in terms of pressure, frequency and other parameters. The lungs in severe TBI subjects have frequently been compromised by direct lung injury and/or acquired ventilator pneumonia and are susceptible to O2 toxicity. It is essential to determine the most effective HBO dose schedule without producing O2 toxicity and clinical complications. This proposed adaptive clinical trial is designed to answer these questions and to provide important data to plan a definitive phase III efficacy trial.				
Objectives:	Objective 1 : (Signal of efficacy) To determine, in subjects with severe TBI, whether there is a >50% probability of hyperoxia treatment demonstrating improvement in the rate of good neurological outcome versus control in a subsequent confirmatory trial.				
	Objective 2 : (Dose selection) To select, in subjects with severe TBI, the combination of treatment parameters (pressure +/- intervening normobaric hyperoxia [NBH]) that is most likely to demonstrate improvement in the rate of good neurological outcome versus control in a subsequent confirmatory trial.				

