9 STATISTICAL CONSIDERATIONS

9.1 STATISTICAL HYPOTHESES

In this phase II clinical trial we hypothesize that there is at least one treatment arm that will demonstrate neurological improvement that warrants further exploration in a confirmatory Phase III trial. The HOBIT trial uses an adaptive design for selecting the combination of hyperbaric oxygen (hyperoxia) treatment dose parameters - pressure and intervening normobaric hyperoxia [NBH]) that provides the greatest improvement in the rate of good neurological outcome versus standard care for subjects with severe traumatic brain injury (TBI). A second goal of this phase II trial is to determine if there is any factor combination of hyperoxia treatment that has at least a 50% probability of demonstrating improvement in the rate of good neurological outcome versus a control (i.e. standard care) in a subsequent phase III confirmatory trial, assuming to be 500 in the control and 500 in the novel arms (Gajewski 2016).

Treatment arms.

There are eight treatment arms defined in the trial:

	Arm	Dose (OTU)
1	Control (1.0 ATA)	N/A*
2	1.5 ATA	260
3	2 ATA	417
4	NBH (100% FiO2 at 1.0 ATA)	540
5	2.5 ATA	592
6	1.5 ATA+NBH	620
7	2 ATA+NBH	776
8	2.5 ATA+NBH	952

*NOTE : In the control arm, subjects will be at 1.0 ATA, however the percent of FiO2 will not be

regulated. Thus, it is theoretically possible that these subjects are accumulating OTUs. For the purposes of this study they will consider the "dose" to be zero and this arm will be modeled separately. The FiO2 will be recorded throughout the study. Subjects will receive at least 21% O2 outside of the chamber, but the level of oxygen supplementation may be higher though not typically exceeding 50%.

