Primary Analysis. The primary analysis is of the GOS-E response at 6 months will use the sliding dichotomy methodology. To assess efficacy, the treatment groups will be compared with respect to the proportion with favorable outcome. The primary analysis will be that a treatment arm is superior to the control arm, meaning that the posterior probability that the rate of response with GOS-E is greater for one experimental arm compared to the control arm. The final analysis will also identify the best treatment arm to advance to a future Phase III trial for confirmation of superiority to the control arm. Specifically, the currently proposed Phase II trial will be considered conclusive if one of the three following cases occur:

1. Early Success: If at any interim analysis the most likely arm has at least a 0.975 posterior probability of being better than control. Minimum subjects enrolled before the study can stop for early success is 116.

2. End of Enrollment Success: If at the conclusion of accrual, the most likely arm has at least a 0.85 posterior probability of being better than control and this same best arm has at least a 0.5 posterior probability of leading to a successful Phase III trial.

3. Early Futility: If at any interim analysis the maximum probability of active dose being better than control by more than 0.10 across all doses is less than 0.10. Minimum subjects enrolled before the study can stop for early futility is 116.

Specific details of the models and assumptions are found in the HOBIT Statistical Analysis Plan.

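### Section 4.1 sends an arm to Phase III on more than 50% predicted success alone, while 9.1 also requires a 0.85 posterior; the stated error rates belong only to the 9.1 rules

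*Protocol*

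**What the plan says.** The protocol describes the step to Phase III in four places.

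- **Section 4.1, Overall Design**, about the most promising arm: "If the probability is > 50%, this treatment arm will be compared for superiority to the control in a future phase III trial". No other condition is attached.
- **Section 1.1, Objective 1** asks "whether there is a >50% probability of hyperoxia treatment demonstrating improvement in the rate of good neurological outcome versus control" in a later confirmatory trial.
- **Section 9.1, second goal**, asks whether any treatment combination "has at least a 50% probability of demonstrating improvement in the rate of good neurological outcome versus a control", with 500 subjects per arm assumed for Phase III. The threshold here is at least 50%; in 1.1 and 4.1 it is more than 50%.
- **Section 9.1, Primary Analysis**, lists three conclusive outcomes. Early success: "If at any interim analysis the most likely arm has at least a 0.975 posterior probability of being better than control". End-of-enrollment success: "the most likely arm has at least a 0.85 posterior probability of being better than control" and, jointly, "this same best arm has at least a 0.5 posterior probability of leading to a successful Phase III trial". Early futility: "the maximum probability of active dose being better than control by more than 0.10 across all doses is less than 0.10".

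Section 9.2 reports a type I error of 0.21 under the complete null and success probabilities of 0.77, 0.92 and 0.98 for small, medium and large effects. The software paragraph in 9.3 says that the early and late success rules were adjusted to bring the type I error to about 20%.

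**The concern.** The decision on Phase III is what this trial is meant to deliver, and the protocol gives its threshold in two ways. An arm with predicted Phase III success above 50% but a posterior below 0.85 goes forward under 4.1 and is not a success under 9.1. Only the 9.1 rules come with operating characteristics. If the two thresholds were nearly equivalent this would be a matter of tidiness. If the 50% condition is clearly weaker, the choice of rule could be made after the results are known, and nobody has stated the false-go rate of the weaker one.

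**Working it through.** **Inputs from the protocol.** Maximum N 200; control rate 0.40 (9.2); Phase III with 500 per arm, thresholds 0.85, 0.5 and 0.975, and the futility rule (9.1); burn-in of 56, response-adaptive allocation, last interim at 176 and final analysis at 200 (6.3).

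**Assumed, because the protocol does not state them.** Phase III tested at one-sided 0.025; a vague prior; for the simulation, the dose-response smoothing, the control share after burn-in and the interim data lag.

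**Step 1. The plan's own figures.** The 0.21 cannot be reproduced exactly without the model in the SAP, which was not available. A simulation used the stated design and a logistic model with a random walk over the active arms in dose order, with 2,000 trials per scenario. The closest setting has random-walk SD 0.25, control share 0.3, and only 26-week completers at interims. The last column keeps the interim rules and replaces the end-of-enrollment criterion by predicted success above 50% alone.

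| Scenario | Stated Pr{Success} | Simulated, 9.1 rules | Simulated, >50% at the end |
|---|---|---|---|
| None | 0.21 | 0.209 | 0.326 |
| Small | 0.77 | 0.786 | 0.857 |
| Medium | 0.92 | 0.911 | 0.947 |
| Large | 0.98 | 0.971 | 0.984 |
| Harmful | 0.08 | 0.078 | 0.134 |

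Success rates agree within 2 points. Mean sample size under the null (173 against 183) and futility (0.34 against 0.29) do not agree, so the last column is approximate.

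**Step 2. Where 50% predicted success falls.** The Phase III standard error is SE3 = sqrt(2 × 0.40 × 0.60 / 500) = 0.031. Predicted success is

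PPoS = Φ((d − 1.96 × SE3) / sqrt(SE² + SE3²)),

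where d is the posterior mean difference and SE its posterior SD. It equals 0.5 at d = 1.96 × 0.031 = 0.061.

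**Step 3. Each threshold translated into the other.** A 0.85 posterior means d = 1.036 × SE. An arm at 50% predicted success has posterior Φ(0.061 / SE).

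| Split | SE | d at posterior 0.85 | PPoS at posterior 0.85 | Posterior at PPoS 0.5 |
|---|---|---|---|---|
| 100 v 100 | 0.069 | 0.072 | 0.56 | 0.81 |
| 40 v 60 | 0.100 | 0.104 | 0.66 | 0.73 |
| 12 v 80 | 0.152 | 0.157 | 0.73 | 0.65 |

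The 100 v 100 split is the most precise that 200 subjects allow. Under these assumptions an arm that reaches 0.85 therefore already has predicted success of at least 0.56. In reverse, 50% predicted success corresponds to a posterior of only about 0.65 to 0.81. With one common response rate p, the factor sqrt(p(1 − p)) cancels, so the last two columns do not depend on the 0.40.

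**Step 4. Does the 0.5 clause bind?** It can bind only if the posterior SD is below 0.061 / 1.036 = 0.059. In the closest null setting it rejected 0 of 297 end-of-enrollment successes. It rejected 3 of 297 with Phase III at one-sided 0.005, and 2 of 292 with a strongly informative prior (logit SD 0.25). At one-sided 0.01 it is borderline by formula and rejected none.

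**Step 5. Size under the null.** From step 1, 0.326 − 0.209 = 0.117: about 12 in 100 null trials would be a go under 4.1 and not a success under 9.1. Across the vague-prior settings whose null success lies within 2 points of 0.21, the go rate under the 4.1 rule is 0.29 to 0.34. In the closest setting it is 0.37, 0.28 and 0.26 with Phase III at one-sided 0.05, 0.01 and 0.005.

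**Step 6. How often the question arises.** By the table in 9.2, 1 − 0.21 − 0.29 = 0.50 of null trials and 1 − 0.08 − 0.53 = 0.39 of harmful-scenario trials meet none of the three listed cases. For these, 4.1 is the only sentence that says what happens to the arm.

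**The case against.** The best defence is that 9.1 is the operative text. It sets out the criteria specifically, and its end-of-enrollment case already contains the 50% condition. Objective 1 and the second goal of 9.1 pose questions and do not make decisions. Only the 4.1 sentence says that an arm will go forward; it is a design summary, and the sentence before it is garbled in the text available. Sections 4.2 and 9.3 add that secondary outcomes also inform the go/no-go decision. This stands to a large extent: it makes the point one of alignment, and the objectives should not be read as rival decision rules. It does not remove the 4.1 sentence, which is unconditional.

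A reader might infer several stronger things that the documents do not support.

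- **That 0.21 is wrong or misattributed.** Section 9.2 ties it to identifying treatments as a success, and 9.3 says which rules were tuned. Nothing claims it for a rule based on 50% alone.
- **That the 0.5 clause can never bind.** That depends on a Phase III significance level the protocol does not state and on a prior it leaves to the SAP.
- **That the lack of a no-go case in 9.1 is an error.** A trial meeting none of the cases is simply not a success, and an inconclusive zone is legitimate in Phase II.
- **That the excess in false go decisions is much larger than found here.** Some simulated settings gave higher rates, but they do not reproduce the stated 0.21.

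**Conclusion.** The point holds as an inconsistency in the stated threshold for advancing an arm. Section 4.1 uses predicted Phase III success above 50% alone. Section 9.1 requires 0.85 and 0.5 at the end of enrollment, or 0.975 at an interim. The type I error and power in 9.2 describe the 9.1 rules and no others. This much rests on the text.

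The size rests on assumptions: 500 per arm in Phase III as stated, a one-sided 0.025 test, a vague prior and an approximate version of the model. Under these, the 0.5 clause rarely or never binds once 0.85 is met. The 4.1 rule taken alone would have a null go rate of roughly 0.3 (about 0.29 to 0.34) against 0.21. The exact figure depends on the model, but the 4.1 rule gave the higher null go rate in every setting tried. This should be fixed in wording; it does not undermine randomization, stopping or the definition of success.

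**What to change.** 1. Rewrite the 4.1 sentence so that an arm is a candidate for Phase III when it meets the 9.1 criteria: early success at 0.975, or end-of-enrollment success at 0.85 together with 0.5 predicted Phase III success.
2. Align Objective 1 and the second goal of 9.1 with this, and use either more than 50% or at least 50% throughout.
3. Keep predicted Phase III success as a reported estimate and an objective; section 3 names it in the primary objective.
4. State in 9.2 that the error rates and power apply to the 9.1 rules. State the Phase III test that defines success, and note that under those Phase III assumptions 0.85 is expected to be the operative threshold.
5. State that when a trial completes enrollment without meeting end-of-enrollment success, no arm is taken forward on the 50% figure alone.

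The cost is a wording amendment, with no change to conduct, sample size or the simulations already reported. If the sponsor instead wants the 50% rule to stand alone, its go probability must be simulated and reported under all five scenarios in 9.2.
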